## Study Run-in period:

We have learnt that medication adherence estmates based on the medication possesson rato (MPR) calculated from prescription refill data are imperfect, and vary substantially when based on 6, 9, or 12 month data. We will therefore have a study run-in period of 4, 8, or 12 weeks by patient choice during which we will determine medication adherence using the MEMScap device on patients who have been determined to have low gout medication adherence (<80%) calculated from pharmacy refill data. Only patients meeting the MPR <80% calculated using MEMScap data will be enrolled in the study and randomized. We will re-consider patients who fail the run-in for future enrollment in the study, when their medication possession ration decreases again.

The study run-in period also allows for a more time for the veterans to review the informed consent and to ask more questions, since veterans would have had from 1-3 months to review the consent form after having signed it, before entering the study.

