## Study procedures at follow-up visits and data collection tools

Follow-up assessments will be done at 1-, 2-, 3-, 4-, 6-, 9-, and 12-months after the baseline visit. The 2- and 4-month visits will be completed via mail, the 3-, 6-, 9-, 12-month visits will be completed in-person lasting 30-60 minutes, and the 1- and 12-month assessments will be completed via phone lasting 15-minutes.

The primary time-point for analyses will be at 6-months. Assessments are kept short considering responder burden and to ensure study retention. Veterans will be provided with \$25 remuneration (VISA gift card or VA Form 10-7078 - Participant payment voucher) for completing the screening visit and each study assessment; an additional \$25 VISA gift card will be provided as VISA gift card or VA Form 10-7078 (Participant payment voucher) to those who perform both blood draws at baseline and 12-month end-of-study visits. If payment voucher is used, participant will bring this voucher to agent cashier to receive \$25 on the same day. 1-month follow-up will be done via a telephone-administered survey at the patient's convenience in their home, given that most assessments are patient-reported. This approach economizes on patient time compared to traditional gout RCTs, where patients are seen in the clinic every 1-3 months with visits lasting 1-3 hours including waiting time (plus travel time). 3-, 6- and 9-month visits will be in-person; MEMSCap data will be downloaded and other outcomes captured. To remind the patient of the follow-up assessments, a post-card (and emails, when applicable) will be mailed 1-week prior and phone call made 2-days prior to the follow-up. To minimize patient responder burden, Veterans are only completing assessments related to primary and select secondary study outcomes (including 4-item gout flare questionnaire at 6- and 12-month follow-up).

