The 12-month visit (end-of-study) will be in-person, similar to the baseline visit. The visit will be coordinated with a scheduled VA clinic visit, as much as possible. MEMSCap data will be downloaded and Veterans will complete a questionnaire assessing gout flares since last visit (including those requiring treatment) and patient satisfaction with treatment, as in 3-, 6- and 9-month follow-up. In addition, Veterans will be requested to get a blood draw for end-of-study sUA (secondary outcome)(32) and also complete GAQ as a gout-specific HRQOL measure and self-reported medication adherence questionnaire (exploratory outcomes). GAQ and sUA will be done only at 12-month follow-up (expected to take additional 30-minutes). Veterans unable to come to the study clinic for the 12-month visit will be offered sUA blood draw at their nearest CBOC (routine laboratory test) and the research associate will administer 12-month assessments via the phone interview.

Statistical Analysis.

- SA1: Improving ULT adherence, directly measured by using MEMS (Medication Event Monitoring System) Caps at 3, 6, 9 months (assess intervention's effect) and 12 months (assess durability of effect),
- SA2: Improving Gout flare rate, patient satisfaction and target serum urate (sUA) <6 mg/dl achievement, as indirect measures of better ULT adherence and important gout outcomes. We will also explore the effect of storytelling on health-related quality of life (HRQOL), self-reported ULT adherence, alcohol ingestion, body mass index (BMI) and gout-related inpatient and emergency room utilization.

For both Aims 1 and 2, descriptive statistics for demographics (age, race, income, marital status, time since diagnosis of gout) and clinical parameters (ULT adherence, # gout flares, satisfaction, serum urate, GAQ) will be examined. Given the two arm study design (storytelling vs. usual care), statistical procedures appropriate for two-group comparisons will be utilized to conduct crude as well as adjusted comparisons based upon the distributional nature of the outcome.

For the primary outcome of ULT adherence, an unadjusted analysis will be conducted using the two-sample ttest to compare ULT adherence across study arms at 3, 6, 9, and 12 months. Adjusted estimates of ULT adherence by study arm controlling for age, gender, income, alcohol, site, and other covariates will be conducted using ordinary least squares regression.

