Similar analyses will be conducted for the secondary outcomes defined in aim 2. When examining sUA level, analyses will also be adjusted for use of other medications that effect serum urate (diuretics, lipid-lowering agents, aspirin and angiotensin receptor blocking drugs etc.), BMI and alcohol use. For frequency of gout flares, analyses will also be adjusted for use of anti-inflammatory prophylaxis during initial ULT treatment. If the normality assumption is violated, nonparametric methods will be used, instead of the parametric tests.

Careful attention will be paid to the distributional assumptions for Poisson regression and methods to adjust for over-dispersion will be employed. Finally, separate logistic regression models will be used to measure treatment differences in the odds of achieving target serum urate <6 mg/dl and odds of healthcare utilization. To analyze the longitudinal data (1-, 3-, 6-, 9- and 12-months), we will use mixed linear models for ULT adherence (continuous outcome) and generalized estimating equations for target serum urate < 6 mg/dl, to analyze temporal relationships between the delivery of the intervention and medication adherence. All analyses will be guided by intent-to-treat analysis principles.

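### Run-in MEMSCap adherence, known before randomisation for every patient, is not a named covariate, and neither the crude nor the adjusted adherence analysis is designated primary

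*Combined protocol and SAP*

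**What the plan says.** **Outcome and time.** The Outcomes section makes MEMSCap-measured ULT adherence the primary outcome. The follow-up section fixes the time: "The primary time-point for analyses will be at 6-months".

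**Analyses.** The Statistical Analysis section says that two-group procedures "will be utilized to conduct crude as well as adjusted comparisons". For the primary outcome it gives two:
- "an unadjusted analysis will be conducted using the two-sample ttest to compare ULT adherence across study arms", at 3, 6, 9 and 12 months;
- an OLS model: "Adjusted estimates of ULT adherence by study arm controlling for age, gender, income, alcohol, site, and other covariates".

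Neither is called primary. The same section replaces parametric tests by nonparametric ones if normality fails, with no test or threshold given. It also plans a mixed linear model for adherence, with no covariates listed, "to analyze temporal relationships between the delivery of the intervention and medication adherence".

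**Baseline value.** The run-in section says: "Only patients meeting the MPR <80% calculated using MEMScap data will be enrolled in the study and randomized". Inclusion criterion 4 repeats the limit. The run-in is a "study run-in period of 4, 8, or 12 weeks by patient choice", and it may be repeated: "We will re-consider patients who fail the run-in for future enrollment in the study".

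**Covariates elsewhere.** Baseline study assessments tags alcohol and BMI as covariates and also as exploratory outcomes. BMI is not in the OLS list for adherence.

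**The concern.** A baseline measurement of the outcome is often among the stronger predictors of the later value. Here it is already collected, on the same device, before randomisation. The plan uses it only to decide entry. The t-test cannot use it, and the OLS model does not name it, although the open end of the covariate list would let it in. The cost is a wider confidence interval than the planned data allow.

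The second issue is what carries the conclusion. The plan offers a crude and an adjusted result for one outcome at one primary time, an adjusted model whose covariates are not fixed, and a possible switch to rank-based methods. If these disagree, nothing in the text says which one counts. A choice made after seeing them would not hold the 5% level.

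**Working it through.** **Inputs from the documents**
- Difference of 6 points, described as an effect size of 0.40 (Table 1). Implied SD = 6 / 0.40 = 15 points.
- 300 patients over three sites (Introduction).
- Dropout: Patient retention cites earlier retention above 80% and allows for a similar magnitude. I read this as 20% dropout.

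**Assumptions, not in the documents:** 1:1 allocation; two-sided 0.05; the correlation r of run-in with month-6 adherence; the R² of other covariates. The documents state no power or type I error, so there is no figure of theirs to reproduce.

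**1. Precision**

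Evaluable per arm: 300 × 0.80 / 2 = 120. Adjusting for one covariate gives residual SD = 15 × √(1 − r²). SE = residual SD × √(2/120). Half-width = 1.97 × SE. Power is from the noncentral t distribution at a difference of 6.

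| r | Residual SD | SE | 95% half-width | Power |
|---|---|---|---|---|
| none (t-test) | 15.00 | 1.936 | 3.8 | 87.0% |
| 0.2 | 14.70 | 1.897 | 3.7 | 88.3% |
| 0.3 | 14.31 | 1.847 | 3.6 | 89.9% |
| 0.4 | 13.75 | 1.775 | 3.5 | 92.0% |

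With no dropout (150 per arm), 93.2% becomes 94.1%, 95.2% and 96.5%.

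The gain on top of the planned OLS model is similar. If its listed covariates explain 10% of the variance (6 covariate degrees of freedom), power is 90.2% and the half-width 3.6 points. Adding run-in adherence at partial r of 0.2, 0.3 or 0.4 gives 91.3%, 92.6% or 94.4%. The interval narrows by 1 − √(1 − r²), that is 2%, 5% or 8%. At R² of 0.10 the listed covariates alone do about as well as run-in adherence alone at r of 0.3, so the listed covariates should stay.

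Selecting patients below 0.80 lowers the correlation. In a normal-model illustration with three assumed run-in distributions, an unselected 0.5 falls to 0.36-0.40. Short run-ins may lower it further.

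**2. Type I error if the version is chosen after the results**

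Under the null and in large samples, the crude and adjusted z statistics correlate at √(1 − R²). The chance that at least one exceeds 1.96 in absolute value is:

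| R² | Correlation of z's | P(either significant) |
|---|---|---|
| 0.04 | 0.980 | 5.9% |
| 0.09 | 0.954 | 6.4% |
| 0.16 | 0.917 | 6.9% |
| 0.25 | 0.866 | 7.3% |

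This covers two fixed versions only. Null simulations went further: 4,000 trials per setting, 240 or 300 patients, run-in correlation 0.3-0.6, listed-covariate R² 0.05-0.10, and four optional covariates each explaining 1-2%. Monte Carlo error is about 0.4 points.
- Best of crude, OLS, and OLS plus run-in: about 6.5-9%.
- Also searching the optional covariates: about 8-12%.
- Also allowing a rank test: about 9-12%.

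**The case against.** **Each analysis is valid on its own.** This stands. The randomised comparison is unbiased with or without the run-in value, and any one prespecified test, the t-test included, holds 5%. A reader might infer that the unadjusted analysis is wrong or biased; the documents do not support that.

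**The t-test comes first, so it leads.** It is the first method named for the primary outcome, and an effect size of 0.40 is a two-group standardised difference. That hints at its status, but the text does not designate it and gives the OLS estimate no lower rank.

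**Both results may be reported.** If so, readers could see a discrepancy. That limits the harm but does not say which result decides.

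**The open list already admits run-in adherence.** It does, so the plan does not exclude it. But a covariate that may enter or not is part of the problem.

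**The precision gain is small and rests on assumed correlations.** This also stands. The case for the change is that it costs almost nothing, not that the trial fails without it.

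**Conclusion.** The point holds as a free improvement with a supporting gap in specification. Run-in MEMSCap adherence is available for every randomised patient and should be a named covariate. Under the stated assumptions, adding it to an unadjusted analysis raises power from 87% to 88-92% and takes the half-width from 3.8 to 3.5-3.7 points, for r of 0.2-0.4. The true correlation is unknown.

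No analysis is named primary, the covariate list is open and the nonparametric switch is undefined. The mixed model does not settle this, since it lists no covariates and is tied to temporal relationships. A result-driven choice between the crude and one adjusted estimate would give about 6-7% type I error at assumed R² of 0.04-0.25, and more if the open list or a rank test were searched as well.

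A reader might infer that the trial's type I error is 6-7%, or at most that. Neither follows. The inflation arises only if the version is picked after the results are seen, which the plan does not say will happen, and the figure is an illustration and not a limit.

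**What to change.** In the Statistical Analysis section:
1. Name as primary the month-6 difference in MEMSCap adherence from the planned OLS model. Use a closed list of pre-randomisation terms: arm, age, gender, income, baseline alcohol, site and continuous run-in MEMSCap adherence. Delete the open-ended phrase from this model.
2. Define run-in adherence as the value over the qualifying run-in that led to randomisation, since run-ins differ in length and may be repeated.
3. State whether baseline BMI is in or out, so that this section agrees with Baseline study assessments.
4. State the window for month-6 adherence (for example, months 0-6 or 3-6).
5. Label the t-test supportive, and limit nonparametric methods to sensitivity analysis for this outcome.
6. Reconcile the study-flow text, which has MEMSCap dispensed at the baseline visit, with the run-in section, which uses it earlier. The former may mean only the follow-up bottle.

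The cost is SAP wording, settled before outcome data are seen by arm. No new patients, visits or measurements are needed.

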With VA HSR&D pilot funding (PPO 14-111), we have completed the development of the storytelling intervention. The purpose of developing the Storytelling Intervention Video in the pilot study was to test it with our subsequent study, which is this fully funded HSR&D merit review. The veterans participating in the intervention video signed the HIPAA Authorization and consent for use of picture and voice. These documents stated that the video recordings will be "analyzed for effectiveness" (as stated in the video recording consent document). The proposed study is to analyze the effectiveness of the intervention video that will "disseminated to other gout patients" (as stated in both HIPAA and Video recording consent documents- **Appendix 1**-highlighted). We will determine the effectiveness of the intervention compared to usual care by conducting a 12-month multicenter randomized controlled trial (RCT) among 150 AA Veterans with gout with a ULT adherence of <0.80 at Birmingham VAMC (total 300 AA Veterans at the 3 proposed VA sites- Birmingham, St. Louis, and Philadelphia VA Medical Centers).

[figure not shown]
Our objective is to test the effectiveness of a patient-centered, culturally relevant narrative intervention, or "storytelling," based on the solid conceptual foundation of the narrative communication theory(19) and the constructs of the Health Belief Model,(20) (HBM) to improve medication adherence and outcomes in chronic diseases among African-Americans (AA), using gout as an example. Gout is a chronic disease associated with chronic symptoms and disability interrupted by intermittent acute flares, similar to Chronic Obstructive Pulmonary Disease (COPD) and Congestive Heart Failure (CHF) that leads to joint destruction if not treated appropriately. Due to the intermittently symptomatic nature of chronic conditions patients, often don't perceive disease severity and susceptibility to disease complications, and, therefore, may not balance the barriers and benefits to medication adherence.(21) Storytelling in the patients' own voice has the power to directly and more effectively confront a patient's barriers to medication adherence, reinforce the benefits and provide useful cues to action.(22) Storytelling promotes patient engagement when the patient identifies with the storyteller and can lead to a patient's recognition of the need to treat the condition and improve health outcomes, as

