## Baseline study assessments.

After the patient has been consented and enrolled in the study, they will then complete the baseline patient assessments using VA Research Electronic Data Capture (REDCap) on IPad. Paper surveys will be used as a backup. Assessments will include the following:

- (1) Demographics: age, gender, income (covariates), marital status;
- (2) Baseline frequency of gout flares requiring treatment and baseline patient satisfaction with ULT treatment;
- (3) Baseline gout-specific HRQOL assessment using the gout assessment questionnaire (GAQ);
- (4) Alcohol use and BMI (covariates; exploratory outcomes since alcohol and higher BMI are associated with higher risk of incident gout, gout flares and higher sUA level (1, 26-28));
- (5) Blood draw for baseline sUA;
- (6) ULT non-adherence on self-reported questionnaire by Voils et al.;(29) and
- (7) Self-reported ULT use from non-VA sites (non-VA ULT use; sensitivity analyses). Patients' usual care serum urate values will be captured at this visit.

Additional information will be obtained including contact information, best time to contact and email address. Veterans will be provided with \$25 remuneration (VISA gift card or VA Form 10-7078 - Participant payment voucher) for completing study assessments at the screening and baseline visit. If payment voucher is used, participant will bring this voucher to agent cashier to receive \$25 on the same day. VA CDW and inpatient/outpatient SAS files assessed through the VINCI database. Medical records databases will be used to assess comorbidity, demographics (marital status) and baseline health care utilization and ULT medication adherence for the last 6-9 months (see eligibility criteria). Patients without DVD players will be provided with a DVD player to watch the DVDs at home at 2- and 4-months.

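### The month-12 comparisons of GAQ and self-reported ULT adherence, both exploratory, do not prespecify the baseline score as a covariate, although it is collected before randomisation

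*Combined protocol and SAP*

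**What the plan says.** **Baseline.** The Baseline study assessments section lists "Baseline gout-specific HRQOL assessment using the gout assessment questionnaire (GAQ") and "ULT non-adherence on self-reported questionnaire". It also says that medical records will supply "baseline health care utilization and ULT medication adherence for the last 6-9 months". The randomisation section places allocation after all baseline assessments are complete, so these are proper pre-randomisation covariates.

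**Follow-up.** At month 12 patients "also complete GAQ as a gout-specific HRQOL measure and self-reported medication adherence questionnaire (exploratory outcomes"). For the GAQ, month 12 is the only follow-up measurement.

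**Analysis.** The primary outcome gets a two-sample t-test at each time point and an adjusted estimate "controlling for age, gender, income, alcohol, site, and other covariates will be conducted using ordinary least squares regression". For Aim 2, "Similar analyses will be conducted for the secondary outcomes defined in aim 2". Extra covariates are then named for serum urate (other medications, BMI, alcohol) and for flares (prophylaxis). For utilization, the text says that "separate logistic regression models will be used to measure treatment differences in the odds of achieving target serum urate <6 mg/dl and odds of healthcare" (the quote stops one word short of the sentence's end) and names no prior-use term. The mixed model and the GEE cover only ULT adherence and target serum urate. GAQ appears elsewhere in the analysis text only among the descriptive statistics.

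**The concern.** An outcome's own baseline value is usually its strongest predictor. Here the trial has already accepted the burden of collecting it, but no comparison between arms is committed to using it.

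Two things are at stake for the two questionnaire scores. The crude comparison of month-12 levels carries avoidable variance and any chance baseline imbalance. In the adjusted model, whether baseline enters is left to a later choice that could be made after the data are seen. The baseline section marks age, gender, income, alcohol and BMI as covariates and gives the two questionnaires no such label, so a reader cannot assume that they belong to the open list.

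**Working it through.** **The plan's own figures.** The documents give no SD, effect size, power or baseline-to-month-12 correlation for GAQ, self-reported adherence or utilization, so there is no figure to reproduce for these outcomes. The nearest inputs are:

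- Sample size: "total 300 AA Veterans at the 3 proposed VA sites" (Introduction). Assuming 1:1 allocation, 150 per arm.
- Dropout: read as about 20% from the Patient retention section, so 0.8 × 150 = 120 evaluable per arm.
- Effect size: 0.40 SD, set in Table 1 for MEMSCap adherence and borrowed here.
- Assumed: two-sided α = 0.05; ρ (baseline to month 12) from 0.3 to 0.7.

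Without a baseline term, a two-sample t-test for 0.40 SD has power 93.2% at 150 per arm and 87.0% at 120 per arm.

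**Continuous scores.** Adding baseline to a linear model multiplies residual variance by 1 − ρ², so the standardised effect becomes 0.40/√(1 − ρ²). At ρ = 0.5 the factor is 1 − 0.25 = 0.75 and the effect is 0.40/0.866 = 0.462. The smallest difference detectable at 80% power is (1.96 + 0.84) × √(2(1 − ρ²)/120) SD (normal approximation), and the equivalent evaluable sample is 240/(1 − ρ²).

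| ρ (assumed) | Variance factor | Power for 0.40 SD, 120 per arm | Detectable at 80% power | Equivalent evaluable patients |
|---|---|---|---|---|
| no baseline term | 1.00 | 87.0% | 0.362 SD | 240 |
| 0.3 | 0.91 | 89.9% | 0.345 SD | 264 |
| 0.5 | 0.75 | 94.6% | 0.313 SD | 320 |
| 0.7 | 0.51 | 99.1% | 0.258 SD | 471 |

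The power gain is therefore 2.9 to 12.1 points. With no dropout (150 per arm), power at ρ = 0.5 goes from 93.2% to 97.9%. For a smaller assumed effect of 0.30 SD at 120 per arm (normal approximation), it goes from 64.2% to 76.5% at ρ = 0.5.

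The comparator in every row is the crude test. Against the plan's adjusted model, ρ should be the partial correlation given age, gender, income, alcohol and site. The documents do not give it, and the gain would be somewhat smaller.

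**Utilization (logistic).** Here 1 − ρ² does not apply, so the effect of a prior-use term was simulated. All inputs are assumed, with 30% prior users in every scenario. Treatment effect: odds ratio 0.45 at 150 per arm, log odds ratio −0.8 at 120 per arm.

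| Scenario | Power without → with prior use | SE of treatment log odds ratio |
|---|---|---|
| 150 per arm, prior-use odds ratio 4 | 64.3% → 67.0% | 0.327 → 0.340 |
| 150 per arm, prior-use odds ratio 8 | 63.5% → 71.5% | 0.292 → 0.325 |
| 120 per arm, prior-use log odds ratio 1.1 | 56.6% → 58.9% | 0.363 → 0.374 |
| 120 per arm, prior-use log odds ratio 1.8 | 57.2% → 62.2% | 0.346 → 0.373 |

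Power rises by about 2 to 8 points, but the standard error rises too. The gain comes from the estimate moving away from zero (in the last row, from −0.726 to −0.832), because the adjusted odds ratio is conditional on prior use.

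**The case against.** - **The covariate list is open.** The adjusted model ends with unspecified other covariates, and baseline could be among them. This stands. A reader might infer that the plan decided to leave baseline out and that precision is certainly lost. The text supports only that baseline is not prespecified; the loss is certain only for the crude comparison.
- **These outcomes are exploratory.** The sentence on similar analyses speaks of Aim 2's secondary outcomes, which the Outcomes section defines as flares, satisfaction and serum urate. This stands and limits the importance. It does not remove the gap: if that sentence does not reach GAQ and self-report, they fall back on the general statement that crude and adjusted comparisons will be made, which names no baseline term either.
- **Utilization.** A reader might infer that its confidence interval is also wider than it need be. The simulations show the opposite for the log odds ratio, so the precision argument does not extend to it.
- **Self-report as the only check on MEMSCap.** A reader might infer that precision matters more because self-report is the only follow-up adherence measure that does not depend on the device. The documents do not support this: the aims and the Outcomes section treat flares, satisfaction and serum urate as indirect adherence measures.
- **Borrowed magnitude.** The 0.40 SD belongs to another outcome and ρ is assumed. If normality fails, the plan switches to nonparametric methods, to which these power figures do not directly apply. All of this stands; the figures are illustrative.

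**Conclusion.** The point holds for GAQ and self-reported ULT adherence, as a gap in prespecification with an inexpensive remedy. Relative to the crude comparison, baseline adjustment would cut residual variance by 9% to 49% for ρ of 0.3 to 0.7. That is equivalent to 24 to 231 extra evaluable patients on top of 240. The size rests on the assumed ρ, 20% dropout, equal allocation and the borrowed 0.40 SD.

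For utilization the benefit is a small power gain under assumed inputs, together with a change in what the odds ratio means. Because the outcomes are exploratory, this is a worthwhile improvement and not a flaw that threatens the trial's conclusions. The same omission affects the secondary outcomes with a month-0 value in Table 1 (flares, SATMED-Q, serum urate), where it matters more.

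**What to change.** In the Aim 2 paragraph of Statistical Analysis, state that month-12 GAQ and self-reported adherence will each be compared by ANCOVA: month-12 score on arm, the same instrument's baseline score, and the covariates already named. State that this adjusted estimate is the reported comparison. Add a simple rule for a missing baseline score, such as mean imputation of the covariate.

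The same sentence can cover SATMED-Q, flares and serum urate, with the baseline value entered in whichever model suits each outcome (linear, Poisson or logistic).

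Optionally, add prior use to the utilization logistic model and say that the odds ratio is then conditional on prior use. The window and type of use need defining: the baseline section refers only to health care utilization and does not limit it to gout-related care, whereas the SA2 outcome is gout-related.

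The cost is a few sentences of analysis text. No new data, visits or patients are needed.

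### Baseline serum urate is collected but named in no serum urate analysis; naming it adds about 3 to 7 points of power at the 20-point target if it correlates 0.5 to 0.7 with month 12

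*Combined protocol and SAP*

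**What the plan says.** All references are to the combined protocol and SAP.

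**Collection.** Table 1 schedules sUA at months 0 and 12. Baseline study assessments lists "Blood draw for baseline sUA" as item 5. The follow-up section offers an extra payment "to those who perform both blood draws at baseline and 12-month end-of-study visits", and states that "GAQ and sUA will be done only at 12-month follow-up", so month 12 is the only follow-up value.

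**Analysis.** For the primary outcome, Statistical Analysis plans a regression "controlling for age, gender, income, alcohol, site, and other covariates", and says the secondary outcomes will be handled in a similar way. When sUA level is examined, "analyses will also be adjusted for use of other medications that effect serum urate (diuretics, lipid-lowering agents, aspirin and angiotensin receptor blocking drugs etc"; the same sentence then names alcohol and BMI. Reaching sUA <6 mg/dl is then assigned to logistic regression, and to generalized estimating equations (GEE) in the longitudinal analysis. The months listed for the longitudinal analysis are 1, 3, 6, 9 and 12.

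**Labels.** Baseline study assessments marks some items as covariates: "Demographics: age, gender, income (covariates), marital status" and "Alcohol use and BMI (covariates; exploratory outcomes". The baseline sUA item carries no such label. The one stated analytic use of baseline sUA that is beyond doubt is the descriptive summary.

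**The concern.** The baseline value of an outcome is often its strongest single predictor. This plan names indirect predictors of urate (BMI, alcohol, aspirin and other drugs) but not the earlier urate measurement, which it already pays to collect. Patients enter after at least six months of prescribed urate-lowering therapy, with no urate threshold for entry. Baseline sUA is therefore an on-treatment value, and some patients may already be below 6 mg/dl. If it predicts month-12 urate to any useful degree, leaving it out gives up precision at no saving.

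Only one of the three named secondary outcomes is affected. Randomisation protects the comparison with or without the covariate.

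**Working it through.** The documents give no power figure for this outcome, so there is nothing to reproduce. The check is the gain in power from adding baseline sUA to the covariates already named.

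**Inputs from the documents**
- 300 patients over three sites (Introduction).
- Dropout of about 20% in the worst case (Patient retention: earlier retention above 80%, similar dropout allowed for). Evaluable: 300 x 0.80 = 240, or 240 / 2 = 120 per arm.
- Target: 20% more patients below 6 mg/dl (Table 1), read as 20 percentage points.

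**Assumptions, because the documents are silent**
- 1:1 allocation and a two-sided 0.05 test.
- Control attainment of 30% or 40%.
- The plan's named covariates, taken together as one index W, explain 10% of urate variance at both times.
- Correlation r between baseline and month-12 sUA from 0.1 to 0.7.

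**Method.** Normally distributed urate at months 0 and 12, with month 12 cut at the threshold; 20,000 simulated trials per scenario. Logistic Wald test for arm, comparing arm + W with arm + W + continuous baseline sUA. What baseline sUA adds beyond W depends on the partial correlation (r - 0.10) / 0.90, which is 0, 0.22, 0.44 and 0.67 for r = 0.1, 0.3, 0.5 and 0.7. The simulation standard error is about sqrt(0.9 x 0.1 / 20,000) = 0.002 near 90% power and sqrt(0.7 x 0.3 / 20,000) = 0.003 near 70%.

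**Power without and with baseline sUA**

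| Control rate | r | 20-point difference | Gain | 15-point difference | Gain |
|---|---|---|---|---|---|
| 0.40 | 0.1 | 0.898 to 0.897 | -0.001 | 0.672 to 0.672 | 0.000 |
| 0.40 | 0.3 | 0.898 to 0.904 | 0.006 | 0.675 to 0.685 | 0.010 |
| 0.40 | 0.5 | 0.896 to 0.929 | 0.033 | 0.671 to 0.727 | 0.056 |
| 0.40 | 0.7 | 0.896 to 0.968 | 0.072 | 0.669 to 0.807 | 0.138 |
| 0.30 | 0.1 | 0.906 to 0.906 | 0.000 | 0.696 to 0.695 | -0.001 |
| 0.30 | 0.3 | 0.910 to 0.917 | 0.007 | 0.699 to 0.711 | 0.012 |
| 0.30 | 0.5 | 0.903 to 0.936 | 0.033 | 0.704 to 0.759 | 0.055 |
| 0.30 | 0.7 | 0.907 to 0.971 | 0.064 | 0.701 to 0.833 | 0.132 |

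Type I error is 0.047-0.052 for either model.

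**As sample size.** The variance of the standardised risk difference falls to about 0.887 of its value at r = 0.5 and 0.717 at r = 0.7. That is like 240 / 0.887 = 271 or 240 / 0.717 = 335 evaluable patients.

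**Sensitivity.** A separate simulation covered control rates from 0.20 to 0.50 at 120 per arm and a 20-point difference. With one other covariate (correlation 0.3 with both urate values) already in the model, the gain was 2-8 points for r of 0.5-0.7; with no other covariate it was 3-10. With 150 per arm and no other covariate it was 2-6. If Birmingham's 150 patients were analysed alone (60 per arm after dropout, control rate 0.30, no other covariate), power would rise from 0.61 to 0.68-0.77.

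**The case against.** **The covariate set is open.** The primary model admits further covariates and the drug list ends in an et cetera. A reader might infer that the plan excludes baseline sUA; the text does not say so. This objection stands. The plan also does not say when the set is fixed, so a choice made after seeing outcomes is a possibility, not something the documents state.

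**The covariate sentence concerns sUA level.** The later logistic sentence for <6 mg/dl lists no covariates. Carrying the list over is a reasonable inference from the instruction to treat secondary outcomes similarly, but it is an inference. On either reading baseline sUA is unnamed.

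**The GEE may bring month 0 in.** With study draws only at months 0 and 12, a repeated-measures model has nothing to repeat unless baseline is used. The month list is loose: it includes month 1, when Table 1 schedules neither MEMS nor sUA. It cannot prove that baseline is left out, and it does not show how baseline would be used.

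**The correlation is unknown.** All patients enter with adherence below 0.80 and the draws are 12 months apart, so urate may track recent dosing and r may be low. This stands, and it is why the gain is given down to r = 0.1, where it is nil.

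**Larger losses and error inflation.** A reader might infer a loss near 14 points at the plan's own target. In the main simulation that figure needs both r = 0.7 and a 15-point difference, which the plan does not state. A reader might also infer an inflated type I error. Reporting the better of the two models would give 0.064-0.066 at r = 0.5 and 0.074-0.075 at r = 0.7, but only if no analysis is designated. The same weakness already exists between the plan's crude and adjusted comparisons. Designating one analysis cures it; the covariate alone does not.

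**Conclusion.** The point holds as a missed gain in precision. Baseline sUA is measured, and no sUA analysis names it. At the protocol's 20-point target the gain is about 3-7 points from about 0.90 if r is 0.5-0.7, and about 1 point or less if r is 0.3 or lower. For a true difference of 15 points it is about 5-14 points at r of 0.5-0.7. These sizes rest on 120 evaluable patients per arm, 30-40% control attainment, and named covariates explaining 10% of urate variance.

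A reader might go further and call the urate comparison biased or invalid. The documents do not support that: the arms are randomised, and simulated type I error is nominal without the covariate. Nor does the point touch the MEMSCap primary outcome. The practical effect is modest, but so little is needed to secure it that the change is worth making before outcome data are examined.

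**What to change.** In Statistical Analysis:

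1. Name continuous baseline sUA as a covariate in the month-12 logistic model for sUA <6 mg/dl, with arm, site and the covariates already listed, all taken at or before randomisation.
2. State that this adjusted model is the analysis that counts for this outcome, and that the crude comparison is supportive.
3. Report the standardised risk difference with its confidence interval beside the odds ratio. Table 1's target is read here in percentage points, and adding a strong covariate changes what the logistic odds ratio estimates.
4. Handle a missing baseline value with a missing-value indicator. Baseline study assessments also says that "usual care serum urate values will be captured at this visit", but Study Population describes the urate measurement itself as a usual-care draw, so the two may be one value. Use a usual-care result as a substitute only where it is a separate measurement.

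The cost is SAP wording and one model term. No new visits, blood draws, data extracts or patients are needed.
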